#### **4.3 Dose Escalation Rules**

The Dose Escalation Phase of this trial will proceed using a conventional 3 + 3 + 3 approach.

If 0 of the first 3 participants treated at a given dose level experience a drug-related DLT during the DLT evaluation period, the dose will be escalated, and 3 participants will be enrolled and treated at the next higher dose level (up to the planned highest dose level).

If 1 of the first 3 participants treated at a given dose level experiences a drug-related DLT, then 3 additional participants will be enrolled at that dose level (thus making a total of 6 participants in this cohort) to further assess the safety of MGC018 alone (Module A) or in combination with MGA012 (Module B).

- If  $\geq 2$  of these 3 additional participants (i.e.,  $\geq 3$  of the 6 participants enrolled in the cohort) experience a DLT, it will be concluded that the MTD has been exceeded, and 3 participants will be enrolled and treated at the next lower dose level.
- If 1 of these 3 additional participants experiences a drug-related DLT, then another 3 additional participants (for a total of 9 participants in the cohort,  $3 + 3 + 3$ ) will be enrolled and treated at that dose level to further characterize the safety of MGC018 alone (Module A) or in combination with MGA012 (Module B).
- If 0 of the 3 additional participants experiences a DLT, then the dose will be escalated, and 3 participants will be enrolled at the next higher dose level.

If  $\geq 2$  participants out of the first 3 participants treated at a given dose level, or  $\geq 3$  of 6 participants treated at a given dose level, or  $\geq 3$  out of 9 participants treated at a given dose level experience a drug-related DLT, then it will be concluded that the MTD for MGC018 alone (Module A) or in combination with MGA012 (Module B) has been exceeded at that dose level, and all subsequent participants will be treated at the next lower dose level.

If  $\geq 2$  participants out of the first 6 participants treated at a given dose level experience the same drug-related DLT, then the enrollment in that cohort will stop, and it will be concluded that the MTD for MGC018 alone (Module A) or in combination with MGA012 (Module B) has been exceeded and all subsequent participants will be treated at the next lower dose level. In categorizing DLTs, all related MedDRA Preferred Terms will be used to determine whether the same DLT has occurred in a given cohort.

If  $\geq 2$  participants out of the first 6 participants treated at a given dose level experience a Grade 4 DLT, then the enrollment in that cohort will stop, and it will be concluded that the MTD for MGC018 alone (Module A) or in combination with MGA012 (Module B) has been exceeded and all subsequent participants will be treated at the next lower dose level.

For participants being treated at a dose level subsequently determined to exceed the MTD for a given cohort of the study, the dose of MGC018 alone (Module A) or in combination with MGA012 (Module B) will be reduced to the next lower dose level as summarized in [Table 3](#) and [Table 4](#). Following these rules for dose escalation, the MTD/MAD will be the highest dose administered during the Dose Escalation Phase of the study at which the incidence of DLT is  $< 33\%$ .

Dose escalation to the next dose level is permitted only after the participants enrolled in the current dose cohort have completed the DLT evaluation period and the safety data have been reviewed by the sponsor medical monitor, Independent Safety Monitor, and the investigators participating in the study. Evaluation of safety data from each cohort will include an assessment of the proportion of participants who receive planned doses, and the percentage of participants that require dose reductions or dose discontinuations for toxicity. The sponsor medical monitor, Independent Safety Monitor and investigators will consider all available data from participants both during and beyond the DLT evaluation period when making dose escalation decisions and in the determination of the recommended phase 2 dose to be evaluated in expansion cohorts. In particular, if a Grade 4 febrile neutropenia has been observed, the sponsor will review and evaluate the safety database for other events of any grade febrile neutropenia prior to making a decision to dose escalate.

At the discretion of the sponsor, dose escalation may be stopped before an MTD is reached. In this case, the MAD may be chosen based on an assessment of PK, pharmacodynamics, biomarker, safety, and response data. An MTD does not have to be reached to expand a dose cohort if the available data demonstrate that a lower dose level may provide antitumor activity while minimizing potential risk. In addition, if an MTD is established, the sponsor may decide to open the Cohort Expansion Phase at a dose lower than the MTD, based on the totality of the PK, pharmacodynamic, biomarker, safety, and response data.

At the discretion of the sponsor, any escalation cohort at a dose level not exceeding the MTD may be expanded to a maximum of 15 participants for further evaluation of safety, PK, and antitumor activity.

When an MTD or MAD is established, any participant remaining on treatment at a lower dose level will be given the option to escalate to the MTD/MAD dose.

#### **4.4 Guidelines for Dose Modification**

Dose modifications are allowed for toxicity related to study drug according to the guidelines in [Section 7](#).

Modification of dose or schedule may be necessitated by the observation of suspected study drug-related AEs. The investigator should use their best medical judgment to safeguard the participant's welfare.

In general, observation of any study drug-related  $\geq$  Grade 3 AE by CTCAE v4.03 should result in suspension of all study drug administration pending evaluation. Reinstitution of assigned study drug administration should be delayed until the study drug-related AE has resolved to  $\leq$  Grade 1 or baseline for that participant (whichever is greater).

If the study drug-related  $\geq$  Grade 3 AE fails to resolve to  $\leq$  Grade 1 or baseline (whichever is greater), causing the participant to miss  $> 2$  scheduled doses of study drug, the investigator should consider whether the participant should be withdrawn from further study drug administration unless there are extenuating circumstances and the investigator reviews the

situation with and receives permission to continue study drug from the medical monitor (refer to **Section 5.4**).

If the participant experiences a second (either similar or different) study drug-related  $\geq$  Grade 3 AE after reinstituting assigned study drugs for a first occurrence of a study drug-related  $\geq$  Grade 3 AE, study drug administration should be delayed. Reinstatement of study drug administration should be delayed until the AE has resolved to  $\leq$  Grade 1 or baseline (from Cycle 1 Day 1, pre-dose) for that participant (whichever is greater), with exceptions noted under **Section 7**. If resolution occurs and the participant misses  $\leq$  2 scheduled dose(s), the investigator upon consultation with the medical monitor may reinstitute study drug.

If the second  $\geq$  Grade 3 study drug-related AE fails to resolve to  $\leq$  Grade 1 or baseline causing the participant to miss  $\geq$  2 scheduled doses of study drug, the investigator should consider whether the participant should be withdrawn from further study drug administration (refer to **Section 5.4**).

If a third possibly, probably, or definitely related  $\geq$  Grade 3 AE occurs, the investigator in consultation with the sponsor's medical monitor should consider whether the participant should be withdrawn from further study drug administration.

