#### **4.4.1 Guidelines for Other Study Drug Related Toxicities**

For all other study drug-related toxicity not listed in **Section 7** dose modifications of study drug may be allowed for participants (see **Table 6** for general guidelines). The investigator should contact the sponsor to discuss the appropriate dose of study drug based on the safety profile and evidence of antitumor activity. Sponsor approval must be obtained in advance of the dose modification of study drug.

For study drug-related  $\geq$  Grade 3 toxicities except fatigue, local reaction, fluid retention, anemia, laboratory abnormalities without clinical significance, and toxicities without serious morbidity to participants, study drug should be held up to 21 days from the planned date of reinfusion until resolution to  $\leq$  Grade 1 or baseline (from Cycle 1 Day 1, pre-dose) for that participant (whichever is greater), then reinstated, if medically appropriate. Any measures such as frozen gloves or socks or scalp cooling cap to prevent cutaneous toxicity or alopecia are left to the investigator's judgment.

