#### 4.4.2 Dose Delays

Participants who experience toxicity should have study drug held pending assessment, management, and resolution of the toxicity. Participants in whom the toxicity is assessed to be unrelated to study drug or for whom the toxicity does not meet the criteria for discontinuation, may reinstitute study drug as per guidelines outlined in [Section 4.4.1](#) and [Section 7](#). Reinstitution of study drug shall be conducted as follows:

- For participants in whom the toxicity is assessed to be related to study drug, dose delays of up to 21 days are allowed.
- For participants in whom the toxicity is unrelated to study drug, dose delays of up to 21 days are allowed. Dose delays up to 4 weeks are allowed for participants who require palliative radiotherapy only in consultation with the medical monitor (see [Section 8.1.1](#)).

- The medical monitor must be consulted prior to the restart of study drug after a dose delay.

A participant with a dose delay > 21 days due to an AE, but who has otherwise experienced clinical benefit, in the judgement of the investigator in consultation with medical monitor, may continue to receive study drug.

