### **5.4 Rules for Study Treatment Discontinuation**

Participants who tolerate treatment may continue to receive treatment with the study drug(s) as specified in the protocol until any one of the following conditions are met:

- Participant meets RECIST v1.1 criteria for disease progression
- Participant meets PCWG-2 criteria for radiographic progression
- Withdrawal of participant due to an AE or SAE
- Withdrawal of participant consent
- Completion of protocol-defined therapy
- Investigator discretion
- Pregnancy
- Occurrence of drug-related DLT or AEs that lead to discontinuation of study drug
- Dose delay > 21 days due to AEs unless approved by the sponsor.
- The sponsor, investigator, or regulatory agency terminates the study
- Death

For individual participants who meet these criteria, but who are otherwise considered to be experiencing clinical benefit in the judgment of the investigator, consideration may be given to continue therapy of MGC018 alone (Module A) or in combination with MGA012 (Module B), for up to maximum of total of 18 cycles (i.e. approximately 2 years), on a case-by-case basis in consultation with the sponsor. If the investigator decides that the participant should be withdrawn from the study or from dosing for any reason other than

disease progression, the sponsor or its designee must be alerted within 24 hours by completing the appropriate electronic case report forms (eCRFs) ([Section 12.2.2](#)).

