## **6 STUDY TREATMENTS**

### **6.1 Description of Treatments**

For Module A, MGC018 will be administered on Days 1 and 22 of each 42-day cycle. For Module B, MGC018 will be administered on Days 1 and 22 of each 42-day cycle. In addition, for Module B, MGA012 will be administered on Day 22 of Cycle 1 and on Days 1 and 22 of every 42-day cycle thereafter. Each cycle is 42 days.

MGC018 will be administered as an IV infusion over 60 minutes. MGA012 will be administered by IV infusion over 60 minutes. On days when the MGC018 and MGA012 are to be administered on the same day (Module B only), MGA012 should be given first, followed immediately thereafter by MGC018. MGC018 and MGA012 will be administered as separate IV infusions.

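### Protocol 4.4 prompts withdrawal for a first unresolved Grade 3 or higher event only beyond about 42 days of delay, while 4.4.1, 4.4.2 and 5.4 work to 21 days

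*Protocol*

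**What the plan says.** **Schedule.** Protocol 6.1: "For Module A, MGC018 will be administered on Days 1 and 22 of each 42-day cycle". Module B gives MGC018 on the same days.

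**Section 4.4, first event.** A related Grade 3 or higher AE that has not returned to Grade 1 or baseline leads to action once there are more than 2 missed "scheduled doses of study drug, the investigator should consider whether the participant should be withdrawn from further study drug administration unless there are extenuating circumstances". The exception also requires that the investigator reviews the "situation with and receives permission to continue study drug from the medical monitor". The text then refers to 5.4.

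**Section 4.4, second and third events.** After a second such event, drug may be restarted, on consultation with the medical monitor, if the event resolves and no more than 2 doses were missed. If it fails to resolve and 2 or more doses are missed, the investigator considers withdrawal, again with a reference to 5.4. A third event prompts that question whatever the delay.

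**Section 4.4.1.** For most related Grade 3 or higher toxicities not listed in Section 7, "study drug should be held up to 21 days from the planned date of reinfusion".

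**Section 4.4.2.** "For participants in whom the toxicity is assessed to be related to study drug, dose delays of up to 21 days are allowed". The medical monitor must be consulted before any restart after a delay. There is an exception: "A participant with a dose delay > 21 days due to an AE, but who has otherwise experienced clinical benefit", as judged by the investigator in consultation with the medical monitor, may continue.

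**Section 5.4.** Among the conditions that end treatment: "Dose delay > 21 days due to AEs unless approved by the sponsor". Continuation for clinical benefit is possible case by case in consultation with the sponsor.

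**The concern.** These passages all answer one question: how long a related severe toxicity may hold up dosing before continued treatment is in doubt. They answer in two units, missed doses and days, and the two do not convert to the same point. The cross-reference from 4.4 to 5.4 does not settle it, because 5.4 contains no missed-dose criterion and 4.4 does not carry the 21-day figure.

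Two things are at stake. One is whether participants with the same toxicity are retreated or stopped on the same basis. The other is how the data are read. Tolerability is part of the primary objective, and Protocol 4.3 makes the percentage of participants needing dose reduction or discontinuation for toxicity an input to escalation and to the choice of expansion dose, using data from beyond the DLT period as well. If the stopping rule is ambiguous, that percentage partly reflects which passage was followed.

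**Working it through.** The plan has no figure to reproduce. The check converts missed doses into days and then sets the passages side by side.

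**Inputs**
- Dosing interval: Day 22 − Day 1 = 21 days, and Day 43 (Day 1 of the next cycle) − Day 22 = 21 days (Protocol 6.1).
- Trigger for a first event: "causing the participant to miss $> 2$ scheduled doses of study drug" (4.4), so at least 3 missed doses.
- Limit in 4.4.1, 4.4.2 and 5.4: 21 days.
- Delay is counted from the planned date of the first dose not given, as in 4.4.1.
- Assumption: scheduled slots stay fixed on the calendar, and a slot passed before restart counts as missed. I found no definition of a missed dose in the protocol.

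**Conversion**

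The k-th missed slot falls 21 × (k − 1) days after the first planned date:
- first: 21 × 0 = 0 days
- second: 21 × 1 = 21 days
- third: 21 × 2 = 42 days

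The number missed for a delay of d days is d/21 rounded up:
- d = 21: 1 missed
- d = 22: 22/21 = 1.05, so 2 missed
- d = 42: 42/21 = 2, so 2 missed
- d = 43: 43/21 = 2.05, so 3 missed

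More than 2 missed doses therefore means a delay of more than 42 days, twice the 21-day limit. The unreconciled window is 42 − 21 = 21 days wide.

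**Side by side, for a related Grade 3 or higher event**

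| Delay | Missed | 4.4, first event | 4.4, second event | 4.4.2 and 5.4 |
|---|---|---|---|---|
| 1–21 days | 1 | no withdrawal prompt | restart possible on resolution | within limit |
| 22–42 days | 2 | no withdrawal prompt | restart possible on resolution; withdrawal also considered | past limit; stop unless an exception applies |
| over 42 days | 3 or more | withdrawal considered | withdrawal considered | past limit; stop unless an exception applies |

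The middle row holds both problems. For a first event, 4.4 read alone asks nothing where 5.4 makes stopping the default. For a second event, a participant whose AE resolves after exactly 2 missed doses meets the restart condition (2 or fewer) and the count for considering withdrawal (2 or more).

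**Routes to continue**
- 4.4, first event: extenuating circumstances plus medical monitor permission, arising only after more than 2 missed doses.
- 4.4.2: clinical benefit, judged by the investigator in consultation with the medical monitor, once the delay exceeds 21 days.
- 5.4: sponsor approval once the delay exceeds 21 days, with a separate case-by-case route for clinical benefit.

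**Scope**

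Section 7 sets its own limits for named toxicities: for example 21 days for Grade 3 or 4 neutropenia (7.4.1) and 28 days for palmar-plantar erythrodysesthesia (7.5). The general rule in 4.4 matters mainly outside those.

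**The case against.** The strongest reply is that the rules differ in kind and can be layered. The 21-day rule is a default stop with a waiver, while the missed-dose rule only asks the investigator to consider withdrawal. On that reading, approval is needed beyond 21 days and the question is asked again beyond 2 missed doses. The second-event overlap could likewise be separated by whether the AE has resolved. Both readings are workable, but the protocol states neither. A participant can also fail to resolve in time for two doses and then resolve, which meets both second-event conditions.

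Other parts of the reply stand, and they defeat stronger readings that a reader might infer:

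- **That the same toxicity would end treatment at one site and not at another.** This does not follow. Section 4.4.2 requires medical monitor consultation before any restart after a delay, and 5.4 requires sponsor approval beyond 21 days. No site may restart on 4.4 alone.
- **That 4.4 permits retreatment which another section forbids.** None of these sections forbids it. Sections 4.4.2 and 5.4 both provide for continuing past 21 days, and 4.1 foresees such delays.
- **That every participant whose event resolves on days 22 to 42 is classified differently.** Section 7 governs many toxicities, the waivers cover others, and for second events 4.4 does raise withdrawal in this window. The documents give no rate from which to count those affected.
- **That the Module A expansion dose is at risk.** Section 4.1.2 records that dose as already determined.

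**Conclusion.** The passages are inconsistent as written. For a first unresolved related Grade 3 or higher AE, the point at which continued treatment comes into question is beyond 42 days in 4.4 and beyond 21 days in 4.4.2 and 5.4, with 4.4.1 also limiting holds to 21 days. A delay of 22 to 42 days falls between them. For a second event, 4.4 does not separate restart from withdrawal at exactly 2 missed doses. The routes to an exception are not aligned.

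The practical effect is limited by mandatory consultation before restart, by the waivers and by the Section 7 limits. What remains is a real possibility of inconsistent handling. It bears on retreatment in both modules, and on the discontinuation-for-toxicity rate as an input to dose decisions in Module B, whose expansion dose still depends on its own escalation. No number of affected participants can be given. The 42-day figure rests on fixed 21-day slots, delay counted from the first planned date, and a passed slot counting as missed. The ±1 day visit windows in the Time and Events Schedules would move it by about a day.

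**What to change.** In the next amendment:
- Reconcile 4.4, 4.4.1, 4.4.2 and 5.4 to one threshold in one unit, either days from the planned dose or missed doses. If doses are used, define when a delayed dose becomes a missed one.
- State one approval route for continuing past that threshold: who decides and on what grounds. If two layered steps are intended, say so.
- Reword the second-event text in 4.4 so that exactly 2 missed doses falls under one rule only.
- Cross-reference the Section 7 limits for named toxicities and say that they take precedence, if that is the intention.

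Which limit is appropriate is for the sponsor and investigators to settle. The cost is protocol wording. No SAP change is needed: SAP 6.3.1, 6.4 and 6.8.1 already report reasons for discontinuation, the number and duration of delays, and AEs leading to delay or discontinuation.

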#### **4.4.1 Guidelines for Other Study Drug Related Toxicities**

For all other study drug-related toxicity not listed in **Section 7** dose modifications of study drug may be allowed for participants (see **Table 6** for general guidelines). The investigator should contact the sponsor to discuss the appropriate dose of study drug based on the safety profile and evidence of antitumor activity. Sponsor approval must be obtained in advance of the dose modification of study drug.

For study drug-related  $\geq$  Grade 3 toxicities except fatigue, local reaction, fluid retention, anemia, laboratory abnormalities without clinical significance, and toxicities without serious morbidity to participants, study drug should be held up to 21 days from the planned date of reinfusion until resolution to  $\leq$  Grade 1 or baseline (from Cycle 1 Day 1, pre-dose) for that participant (whichever is greater), then reinstated, if medically appropriate. Any measures such as frozen gloves or socks or scalp cooling cap to prevent cutaneous toxicity or alopecia are left to the investigator's judgment.

**Table 6 Guidelines for Other Study Drug Related Toxicities**

| Adverse Event Severity Grade | MGC018 Management Guidelines                                                                                                                                                                                                                                                                           | Medical Care Guidelines                                                                                                                                                                                                                                                                                                                 |
|------------------------------|--------------------------------------------------------------------------------------------------------------------------------------------------------------------------------------------------------------------------------------------------------------------------------------------------------|-----------------------------------------------------------------------------------------------------------------------------------------------------------------------------------------------------------------------------------------------------------------------------------------------------------------------------------------|
| 1                            | No dose modification necessary. Consider delaying dose of MGC018 until < Grade 1 or baseline (from Cycle 1 Day 1, pre-dose) for that participant (whichever is greater). Consider dose reduction of one dose level.                                                                                    | Consider clinical evaluation of the participant once weekly or every other week to monitor. Obtain clinical laboratory evaluations as indicated e.g., weekly CBC, chemistry.                                                                                                                                                            |
| 2                            | Consider delaying dose of MGC018 until $\leq$ Grade 1 or baseline (from Cycle 1 Day 1, pre-dose) for that participant (whichever is greater). Consider dose reduction of one dose level.                                                                                                               | Consider clinical evaluation of the participant once weekly or every other week to monitor. Obtain clinical laboratory evaluations as indicated e.g., weekly CBC, chemistry.                                                                                                                                                            |
| 3                            | Delay dose of MGC018 until $\leq$ Grade 1 or baseline (from Cycle 1 Day 1, pre-dose) for that participant (whichever is greater). Consider dose reduction of one or two dose levels. If the same event $\geq$ Grade 3 recurs consider study drug discontinuation.                                      | Consider hospitalization. Consider clinical evaluation of the participant $\geq$ 1 time per week or every week to monitor. Perform imaging and/or other evaluations to determine the etiology of the event. Obtain clinical laboratory evaluations as indicated e.g., weekly CBC, chemistry.                                            |
| 4                            | Delay dose of MGC018 until $\leq$ Grade 1 or baseline (from Cycle 1 Day 1, pre-dose) for that participant (whichever is greater). Consider dose reduction of one or two dose levels. Consider study drug discontinuation. If the same event $\geq$ Grade 3 recurs consider study drug discontinuation. | General guidance includes hospitalization and emergent medical care. Perform imaging and/or other evaluations to determine the etiology of the event. Consider clinical evaluation of the participant $\geq$ 1 time per week or every week to monitor. Obtain clinical laboratory evaluations as indicated e.g., weekly CBC, chemistry. |

Abbreviations: CBC: complete blood count.

